 - Study the effectiveness of celecoxib (Celebrex) in the reduction of orbital inflammation in patients with thyroid eye disease.
 - Primary outcome- reduction of clinical activity (by Clinical Activity Score (CAS) and VISA score (Vision, Inflammation, Strabismus, Appearance))
 - Secondary outcomes- improvement in proptosis, strabismus, and eyelid retraction, and TED quality of life questionnaire

3. Background

Date: January 21, 2017 Principal Investigator: [name] Application Number: IRB00094787

- Thyroid eye disease (TED) occurs in up to 50% of patients with Graves disease and to a lesser 0 extent in Hashimoto thyroiditis. Autoantibodies to the TSH receptor [thyroid stimulating immunoglobulin (TSI) and TSH receptor antibody (TSHR Ab)] have cross-reactivity with similar antigens on the surface of orbital cell membranes. The basic pathogenesis of TED involves a cell-mediated inflammatory process that attacks orbital soft tissues, including adipocytes, fibroblasts, and extraocular muscle. Their binding results in recruitment of T-cells and monocytes (and B-cells to a lesser extent) and secretion of inflammatory cytokines. After an acute inflammatory phase, a chronic condition results from persistent tissue changes including extraocular muscle fibrosis and fat hypertrophy. Vision problems result when adipocyte proliferation leads to proptosis and corneal exposure, and extraocular muscle enlargement in addition to adipogenesis can cause compressive optic neuropathy. Proptosis is also disfiguring and can be remedied only by surgery after the inflammatory phase resolves; this can take 1-2 years without any medical intervention. Chronic TED responds only to surgical correction, and treatment in the acute phase can reduce morbidity. Current treatments of active TED involve nonspecific anti-inflammatory medications such as corticosteroids (with the attendant side effects) and orbital radiotherapy (controversial because of limited data supporting efficacy and theoretic risk of secondary malignancy). Recently, rituximab has been used in severe cases, but its expense and side effect profile have limited its utility.

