- Outcomes: The primary study outcome is reduction of clinical activity of TED, as determined by both the CAS and VISA scores. We will use both scales because there is currently disagreement as to which scale serves as a better overall assessment tool. Secondary outcome measures will include reduction of specific aspects of TED, including proptosis, diplopia, and eyelid retraction, as well as a validated TED-specific quality of life survey. These elements are captured in part by the 2 scales but also will be evaluated separately. Comparison of our primary and secondary outcomes between the treatment and control groups and with published studies of steroid treatment for TED may provide us with an indication of the relative efficacy of celecoxib treatment and whether further study is warranted. Treatment safety also will be assessed, and adverse events recorded. A recent prospective study of intravenous corticosteroid dosing for TED reported major adverse events in 10/159 (6.3%) of subjects and minor adverse events such as gastric distress, mild BP increase not requiring medication, and local skin reactions in about 25% of subjects. We anticipate a lesser incidence of minor or major adverse events based on the side effect profile of celecoxib in patients without co-morbidities placing them at higher risk (most TED patients are young and otherwise healthy). Occurrence of adverse events at a rate

greater than what has been reported for intravenous corticosteroid (an accepted method of TED treatment) would suggest that risk of celecoxib treatment exceeds any benefit.

- Biospecimens will be collected in this study, to include urine for a pregnancy test for female patients of childbearing age to determine eligibility, as well as blood as noted above that will be drawn by the clinical lab.
- Study length: Subjects will be followed for 12 months.
- Safety monitoring: As noted, baseline blood testing and phone surveillance will be performed. If abnormal results are found during drug treatment, then subjects will be advised to stop the medication and will be examined by the PI or other MD investigator. Adverse events will be reported to the IRB per institutional policy.
- Subjects may be taken out of the study if:
 - Staying in the study would be harmful.
 - Treatment required is not allowed in the study.
 - Those that fail to follow instructions.
 - Subjects become pregnant.
 - The study is cancelled.

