The primary study outcome is reduction of clinical activity of TED, as determined by both the CAS and VISA scores. We will use both scales because there is currently disagreement as to which scale serves as a better overall assessment tool. Secondary outcome measures will include reduction of specific aspects of TED, including proptosis, diplopia, and eyelid retraction. These elements are captured in part by the 2 scales but also will be evaluated separately. Change in quality of life will be measured by a validated questionnaire as another secondary outcome measure. Comparison of our primary outcomes between treatment and control groups will provide us with an indication of the relative efficacy of celecoxib treatment. Treatment safety also will be assessed, and adverse events recorded. A recent prospective study of intravenous corticosteroid dosing for TRO reported major adverse events in 10/159 (6.3%) of subjects and minor adverse events such as gastric distress, mild BP increase not requiring medication, and local skin reactions in about 25% of subjects. We anticipate a lesser incidence of minor or major adverse events based on the side effect profile of celecoxib in patients without co-morbidities placing them at higher risk (most TED patients are young and otherwise healthy). Occurrence of adverse events at a rate greater than what has been reported for intravenous corticosteroid (an accepted method of TED treatment) would suggest that risk of celecoxib treatment exceeds any benefit. Observation of adverse events in excess of this rate during the treatment phase would require review, and consideration of early study termination. The changes in either the CAS or VISA score will be compared between the celecoxib and observation groups to determine whether a trend or significant difference can be found.

8. Risks

The study procedures, apart from the proposed treatment, carry no risk beyond that of standard clinical care. Celecoxib has well-described risks especially in certain patient populations, who will be excluded from this study as noted. Below is an enumeration of risks copied from the package insert:

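### Section 7 does not say at which visit, at what level, or on one scale or both a celecoxib effect on CAS and VISA would count as shown

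*Combined protocol and SAP*

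**What the plan says.** Section 2 (Objectives) lists two instruments under one primary outcome: "Primary outcome- reduction of clinical activity (by Clinical Activity Score (CAS) and VISA score". Sections 4 and 7 repeat it in sentence form: "The primary study outcome is reduction of clinical activity of TED, as determined by both the CAS and VISA scores". Both sections give the reason for having two: "We will use both scales because there is currently disagreement as to which scale serves as a better overall assessment tool".

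The analysis is a single sentence at the end of Section 7: "The changes in either the CAS or VISA score will be compared between the celecoxib and observation groups to determine whether a trend". Its stated aim is "to determine whether a trend or significant difference can be found".

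Section 4 schedules full examinations at baseline and at months 1, 3, 6 and 12, with both scores derived from the examination. Treatment lasts 3 months. Section 5 sets an entry floor of 3 on CAS and a target of 40 participants.

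On how the result will be used, Section 7 says: "Comparison of our primary outcomes between treatment and control groups will provide us with an indication of the relative efficacy of celecoxib treatment". Section 4 is wider: it draws also on the secondary outcomes and on published steroid studies, and says that the comparison "may provide us with an indication of the relative efficacy of celecoxib treatment and whether further study is warranted".

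**The concern.** The outcome is worded with *both* and the comparison with *either*, and neither word is a decision rule. *Both* may mean only that two scales are recorded; *either* may mean each in turn. On any of these readings, the plan does not say what is concluded if CAS differs between arms and VISA does not. That split is plausible, because the sponsor uses two scales precisely since it is disputed which one assesses the disease better.

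Three further choices are open: which of the four post-baseline visits is primary, what level counts as significant, and what a trend is. A trend stands beside a significant difference as something the comparison may find, with no definition and no stated consequence.

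At stake is whether the same 40 patients are reported as a positive or a negative study according to a rule picked after the results are known. A smaller matter is that the sentence compares raw changes. This is valid in a randomised trial, but it may leave unused some of the precision available from the baseline scores.

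**Working it through.** **Plan's own figure.** The only design number is the target of 40. It comes with no effect size, SD, level or power, so it cannot be reproduced.

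**Inputs.** From the documents: 40 patients, two scales, four post-baseline visits, CAS entry floor of 3, CAS range 0-7 and VISA range 0-16 (Sections 4 and 5). Assumed, because the documents are silent: 1:1 allocation (20 per arm), two-sided 5% per test, and correlation between the two scales' change scores of 0.5 to 0.8.

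**Step 1: false leads at one visit.** Let p = 2.5% be the null chance that one scale is significant in celecoxib's favour. For two scales,

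P(at least one) = 2p − P(both).

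- If the scales were independent: P(both) = 0.025² = 0.06% and P(at least one) = 1 − 0.975² = 4.9%.
- If they were perfectly correlated, both equal 2.5%.
- Simulated t tests (38 df, 200,000 trials per setting) at scale correlation 0.5 / 0.8: both 0.43% / 1.07%; at least one 4.5% / 3.9%.
- Check by the identity: 5.0 − 0.43 = 4.6% and 5.0 − 1.07 = 3.9%, which agrees within simulation error.
- At least one scale after Holm correction at an overall 5%: 2.3% / 2.0%.

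The two natural readings therefore lie on opposite sides of the nominal 2.5%.

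**Step 2: what each rule does to power.** With 20 per arm, the smallest effect detectable on one scale with 80% power is 0.91 SD, so 0.9 SD is used as a reference. Change scores, scale correlation 0.7:

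| Assumed true effect | Either, uncorrected | At least one, Holm | Both |
|---|---|---|---|
| 0.9 SD on both scales | 88% | 81% | 70% |
| 0.6 SD on both scales | 59% | 46% | 33% |
| 0.9 SD on one scale, none on the other | 79% | 70% | 2.5% |

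The last row shows why the choice must be explicit: if only one scale responds, the rule settles the outcome.

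**Step 3: baseline adjustment.** With equal SDs σ and baseline-to-follow-up correlation r, the variance per patient is 2σ²(1 − r) for change and σ²(1 − r²) under ANCOVA. The ratio is (1 + r)/2, which is 0.65, 0.75 and 0.85 at r = 0.3, 0.5 and 0.7. This textbook ratio ignores the CAS floor and the cost of estimating the slope. Simulating rounded scores with 20 per arm and baseline CAS of at least 3 (r = 0.3 to 0.7, equal SDs):

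- CAS ratio 0.775-0.972, so variance falls by about 3-23%.
- VISA ratio 0.677-0.918, so variance falls by about 8-32%.
- At r = 0.9 with equal SDs the CAS ratio is about 1.0. With follow-up SD 1.3 to 1.5 times baseline and r = 0.7 to 0.8, ratios are about 0.98-1.04. The gain disappears, and the worst loss is about 4%.

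**The case against.** **The study promises little.** It is small, speaks only of an indication, and openly looks for a trend. This stands and lowers the stakes. It does not supply a rule: an indication still has to be read from something, and Section 4 ties it to the question of further study. A reader might infer that this comparison alone decides that question. The documents do not say so. Section 4 also brings in the secondary outcomes and published steroid studies, and safety is assessed as well.

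**Multiple visits.** A reader might infer that a significant difference on either scale at any visit would count. Under that rule, with visit correlation assumed at 0.3 to 0.7, the null chance would be 10-15% favouring celecoxib and 20-30% counting both directions. No section states such a rule. The error rate would be higher if several visits could count, but these figures do not measure the plan as written.

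**Which rule was meant.** A reader might take *either* as a commitment to an at-least-one rule, or *both* as a commitment to require agreement. The text supports neither firmly, and disagreement over the better scale can be argued both ways: neither scale should be privileged, or the two should concur. The choice belongs to the sponsor.

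**Change scores.** It would be too strong to call the change-score comparison wrong, or ANCOVA always more precise. Randomisation makes the change comparison valid. The gain depends on SDs and a correlation that the documents do not give, and a wider follow-up spread is plausible because Section 8 expects some untreated patients to improve and others to progress. What stands is that ANCOVA is a sensible default with a small worst-case cost.

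**Incompleteness.** The wording proposed here does not settle the analysis set or missing data. That is a fair limit of this point.

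**Conclusion.** The point holds as an omission. The plan fixes no visit, no level, no meaning for a trend and no one-or-both rule, and no other section fills the gap. This part rests on no assumption.

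Its size does rest on assumptions: two-sided 5% per test, 20 per arm, scale correlation 0.5-0.8. At a single visit, the null chance of a significant result favouring celecoxib is 3.9-4.5% if either scale suffices and 0.4-1.1% if both must differ, against 2.5%. The inflation under the looser reading is modest. The larger problem is that the reading can be chosen afterwards.

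Baseline adjustment is a secondary improvement, likely but not guaranteed to help. The consequence is an unreliable lead from an exploratory trial, which should be fixed before outcome data are examined.

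**What to change.** Replace the last sentence of Section 7 with:

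> Primary analysis: between-arm difference in CAS and in VISA at month 3 (end of treatment), each by ANCOVA adjusted for the baseline score of the same scale, two-sided. Months 1, 6 and 12 are supportive and reported with 95% confidence intervals. Any trend is descriptive only.

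The sponsor may name one other visit instead, before outcome data are seen; the Abstract also seeks an effect on later fibrotic changes.

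Add one of two success rules, offered on equal footing and chosen by the sponsor before outcome data are seen:

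- (a) a significant difference favouring celecoxib on both scales, each at 5%, with no correction; or
- (b) a significant difference favouring celecoxib on at least one scale after Holm correction at an overall 5%.

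Then align *both* and *either* in Sections 4 and 7 with the rule chosen.

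**Cost.** No patient, visit or measurement is added, because both scores come from examinations already scheduled, including baseline. The price is power relative to an uncorrected either-scale reading of change scores: at 0.9 SD on both scales, from about 88% to 81% under (b) or 70% under (a). Rule (a) has almost no chance of success if only one scale responds. With equal SDs and r = 0.3 to 0.7, ANCOVA roughly offsets the Holm cost (81-92%, against 82-90% for uncorrected change scores in the same simulations), but this should not be relied on if follow-up scores spread out.

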exam to evaluate the potential subject's optic nerve. Photographs (external, eye movements, optic nerve) may be taken as needed. This eye examination is standard of care on any thyroid eye disease patient. Findings from the eye exam will be used to determine a CAS and VISA score. The CAS takes into account 7 manifestations (spontaneous retrobulbar pain, pain with eye movement, eyelid erythema, eyelid edema, conjunctival injection, chemosis, and caruncular swelling) with 1 point assigned for each positive finding. The VISA score ranges from 0-16 based on findings related to inflammation, strabismus, and eyelid changes and proptosis (appearance). Both scales were developed to assess features of active disease that might change with treatment.

- Study subjects will be randomly assigned to observation with no prescription treatment, or treatment with oral celecoxib 100 mg twice daily for 3 months. Patients will have a full clinical exam at baseline, 1 month, 3 months, 6 months, and 12 months, with additional clinical visits more frequently if indicated by disease course/activity. The proposed frequency of clinic visits is within standard of care for newly diagnosed active-phase TED.
- For those subjects randomized to the treatment group, baseline blood testing for blood counts, renal and hepatic function (BUN, Cr, AST, ALT, total bilirubin) will be obtained prior to starting the drug. Testing will be performed by a standard clinical laboratory and billed to insurance. Testing will be repeated at 1mo and 3mo after randomization/initiation of therapy for those receiving celecoxib. Abnormal BUN or creatinine (outside normal range) on lab testing or any previous/current kidney disease will be the criteria for labeling a patient as having impaired renal function. Abnormal liver enzymes (AST, ALT, bilirubin outside normal range) or previous/current liver disease will determine whether a patient is labeled as having impaired hepatic function. Monthly phone interviews also will be conducted by physician study team members to determine if other side effects, such as edema, may be occurring. Subjects will be asked specifically about peripheral swelling, any blood in urine or skin discoloration, or changes in exercise tolerance. Positive responses will trigger an unscheduled visit with the PI or co-investigator MD. Patients will be cautioned not to take additional NSAID medications while on Celecoxib, as this may increase the chance for adverse effects.

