 - There may be other reasons to take subjects out of the study that we do not know at this time.

5. Inclusion/Exclusion Criteria

Eligibility criteria:

- *Recent diagnosis of thyroid eye disease (within the past 6 months)*
- Have ocular symptoms or signs of TED with a CAS score of at least 3
- Ages 18-80 years

Exclusion criteria:

- Pregnancy
- Previous treatment with corticosteroid for TED for >2wks
- Previous treatment with orbital radiation for TED
- Impaired renal function
- Impaired hepatic function
- *Treatment with antihypertensive medications except beta-blockers*
- History of congestive heart failure, cardiac valvular disease, or coronary artery disease
- Allergy to NSAID or previous adverse reaction (ie. GI bleeding)
- Vision loss due to compressive optic neuropathy

Target 40 participants will be enrolled in this study.

6. Drugs/ Substances/ Devices

Celecoxib (Celebrex) is a non-steroidal anti-inflammatory drug approved by the Food and Drug Administration (FDA) for the treatment of pain, osteoarthritis, rheumatoid arthritis, and ankylosing spondylitis. We will be using the recommended dosage of 100 mg twice a day over the course of 3 months. Celecoxib for TED is an off-label usage.

7. Study Statistics

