- **Cardiovascular warning:** All prescription NSAIDs, like CELEBREX, ibuprofen, naproxen, and meloxicam have the same cardiovascular warning. They may all increase the chance of heart attack or stroke that can lead to death. This chance increases if you have heart disease or risk factors for it, such as high blood pressure or when NSAIDs are taken for long periods. Congestive heart failure and peripheral edema has also occurred in some patients has also been noted.
- CELEBREX should not be used right before or after certain heart surgeries.
- Stomach and intestine risk: All prescription NSAIDs have the same warning for serious stomach and intestine problems: They may cause ulcers and bleeding, which can occur without warning and may cause death.
- **Renal warning:** Long term use of NSAIDs, like CELEBREX, have resulted in renal papillary necrosis. Patients at risk are those with impaired renal function, heart failure, liver dysfunction, those taking diuretics, ACE inhibitors, and angiotension II inhibitors.

Date: January 21, 2017 Principal Investigator: [name] Application Number: IRB00094787

• Serious skin and allergic reactions can occur with CELEBREX. CELEBREX shold not be taken if one has had an asthma attack, hives, or other allergies to aspirin, other NSAIDs, or certain drugs called sulfonamides.

Risks of corticosteroid treatment are noted in section 7 with at least 25% of patients experiencing a minor or major adverse event. Orbital radiotherapy carries theoretic risk of ocular radiation toxicity (cataract formation, radiation retinopathy or optic neuropathy) and second malignancy occurrence, but the actual rate of such events is not known. Untreated, some patients with TED may have spontaneous improvement while others will progress to more severe manifestations. Increased disease activity at presentation is a predictor for progression, and we thus are including only subjects with clinical activity that may put them at risk for such changes. Treatment is effective only during the active phase of TED, and observation may result in irreversible proptosis or strabismus requiring subsequent surgery.

9. Benefits

The major benefit of the study is anticipated to be reduction of TED severity as measured by clinical activity assessment.

10. Payment and Remuneration

Subjects will not be compensated for participation.

11. Costs

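### Section 7 prespecifies no baseline covariate for the CAS and VISA comparisons, although both scores are taken at baseline and Section 8 treats presenting activity as prognostic

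*Combined protocol and SAP*

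**What the plan says.** Section 7 (Study Statistics) makes reduction of clinical activity on both CAS and VISA the primary outcome. Its only statement of how the arms will be compared is "The changes in either the CAS or VISA score will be compared between the celecoxib and observation groups". It names no test, model, covariate, alpha or analysis visit.

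The baseline values will exist. Section 4 (Study Procedures) states "Patients will have a full clinical exam at baseline, 1 month, 3 months, 6 months, and 12 months" and, of the scores, "Findings from the eye exam will be used to determine a CAS and VISA score".

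On allocation, Section 4 says "Study subjects will be randomly assigned to observation with no prescription treatment" or to celecoxib. It gives no ratio and no stratification by baseline activity.

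Section 8 (Risks) says "Increased disease activity at presentation is a predictor for progression" and uses this to justify restricting entry. Section 5 applies the restriction, "Have ocular symptoms or signs of TED with a CAS score of at least 3", and sets the size: "Target 40 participants will be enrolled in this study".

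**The concern.** The protocol relies on baseline activity to choose its patients but does not say how the analysis will use it. Section 7 does not exclude adjustment; it leaves it open.

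A change score does use baseline, by subtraction. Subtraction is fully efficient only if each extra point at baseline carries through as one extra point at follow-up. Otherwise change still depends on baseline. The comparison then carries avoidable noise, and a chance difference between arms at baseline passes partly into the result.

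Two things are at stake with 40 patients. The first is precision, which is already limited. The second is that an unspecified choice between adjusted and unadjusted results can be made after both have been seen.

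**Working it through.** **Inputs from the documents.** Total N = 40 (Section 5). CAS has seven one-point items (Section 4) and entry needs at least 3 (Section 5), so baseline CAS lies between 3 and 7. VISA runs from 0 to 16 (Section 4) with no entry limit. There is no sample-size calculation behind the 40, so there is no figure of the plan's own to reproduce.

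**Assumptions (not in the documents).** 1:1 allocation, so 20 per arm. Correlation ρ between baseline and follow-up of 0.3, 0.5 or 0.7. k = baseline SD / follow-up SD of 1.0, 0.8 or 0.7; values below 1 represent a baseline spread narrowed by the entry threshold. Two-sided alpha 0.05. True effect 0.8 follow-up SD. As a sensitivity case, 15% loss, giving 20 × 0.85 = 17 per arm. Section 4 lists grounds for removal ("Subjects may be taken out of the study if") but gives no rate.

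**Step 1: variances.** In units of follow-up variance, per patient:

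- change score: 1 + k² − 2ρk
- ANCOVA: (1 − ρ²) × (1 + 1/(N − 4)), where the last factor is the expected price of estimating the slope

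Ratio of ANCOVA to change score = (1 − ρ²)(1 + 1/(N − 4)) / (1 + k² − 2ρk).

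Example with N = 40, k = 1, ρ = 0.5: 0.75 × (37/36) / 1 = 0.771.
Example with N = 40, k = 0.7, ρ = 0.7: 0.51 × (37/36) / 0.51 = 1.028. Here the true slope ρ/k is exactly 1, so adjustment has nothing to recover and costs only the 1/36.

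**Step 2: error from a chance imbalance.** A baseline difference of D baseline SDs leaves an error of (k − ρ)D follow-up SDs in the change-score difference. Example with k = 1, ρ = 0.3, D = 0.5: 0.7 × 0.5 = 0.35.

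**Step 3: results.** Power comes from 40,000 simulated bivariate-normal trials per cell, t-test on change against ANCOVA, 20 per arm. The simulated variance ratios agree with the formula to within 0.006.

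| k | ρ | Variance ratio, N = 40 | Variance ratio, N = 34 | Power, change | Power, ANCOVA | Error if D = 0.5 |
|---|---|---|---|---|---|---|
| 1.0 | 0.3 | 0.668 | 0.672 | 55% | 72% | 0.35 |
| 1.0 | 0.5 | 0.771 | 0.775 | 70% | 80% | 0.25 |
| 1.0 | 0.7 | 0.874 | 0.878 | 89% | 93% | 0.15 |
| 0.8 | 0.3 | 0.806 | 0.811 | 63% | 72% | 0.25 |
| 0.8 | 0.5 | 0.918 | 0.923 | 77% | 80% | 0.15 |
| 0.8 | 0.7 | 1.008 | 1.013 | 93% | 93% | 0.05 |
| 0.7 | 0.3 | 0.874 | 0.879 | 67% | 72% | 0.20 |
| 0.7 | 0.5 | 0.976 | 0.981 | 79% | 80% | 0.10 |
| 0.7 | 0.7 | 1.028 | 1.033 | 93% | 93% | 0.00 |

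**Step 4: how likely is an imbalance?** The standard error of the baseline difference is √(2/20) = 0.316 SD. The chance of a difference above 0.3 SD in either direction is 0.343, and above 0.5 SD it is 0.114. At 17 per arm the standard error is √(2/17) = 0.343 SD and the chances are 0.382 and 0.145.

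**Step 5: Steps 1 and 2 describe one loss.** Since 1 + k² − 2ρk = (1 − ρ²) + (k − ρ)², the extra variance of the change score is exactly the average squared imbalance error. The last column therefore shows the same loss, conditional on an imbalance of 0.5 SD. It should not be added to the variance ratio.

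**The case against.** The strongest reply is that nothing here is wrong. Comparing changes between randomised arms is valid, it already takes baseline into account by subtraction, and its ordinary standard error covers chance imbalance. That is correct. The point is about efficiency and prespecification, not bias.

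Several further objections have weight.

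- **Prognostic evidence.** The Section 8 statement concerns progression and serves to justify the entry rule. It does not show that baseline CAS predicts follow-up CAS among patients already at 3 or more, and it says nothing specific to VISA. It supports adjustment without supplying a correlation.
- **Uncertain gain.** In four of the six cells with k below 1, power moves by three points or less. The largest benefit (55% to 72%) needs equal SDs and ρ = 0.3.
- **VISA.** It has no entry limit of its own, but its inflammation component is indirectly restricted by the CAS rule. Its strabismus and appearance components may track closely over time, and a high correlation shrinks the gain: with equal SDs the ratio is 0.95 × (37/36) = 0.976 at ρ = 0.9. A larger gain for VISA than for CAS is plausible, not established.
- **Distribution.** CAS is a short count with a floor at 0, so power from normal data is indicative only.
- **Scope.** This is one part of a thinner problem: Section 7 names no test, alpha or visit, in a small exploratory study.

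These limit the claimed size and argue for modest weight. They do not make adjustment unsound, and the wider gap does not close this one. Because the possible loss is tightly bounded and the possible gain is not, the recommendation does not depend on knowing ρ or k.

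**Conclusion.** The concern holds. Section 7 specifies a comparison of changes and no baseline adjustment, while the covariate is collected and the protocol itself regards it as prognostic. The unadjusted comparison is unbiased on average; what is lost is precision and a firm prior choice of analysis.

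Over the assumed range at 20 per arm, ANCOVA has between 0.67 and 1.03 times the variance of the change-score comparison. For CAS, if the threshold does narrow the baseline spread (k of 0.7 or 0.8), this means anything from a saving of about a fifth to a loss of about 3%; a larger saving requires that it does not. Every one of these sizes rests on assumed SDs, correlation, effect, alpha, allocation and, for the 17-per-arm case, attrition. The absence of any stated adjustment or stratification rests on the text alone. This is a change the sponsor should make, though the trial remains valid without it.

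**What to change.** Add to Section 7:

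> CAS and VISA will each be compared between arms by ANCOVA, with arm and the baseline value of the same scale as covariates; the adjusted mean difference and 95% CI will be reported.

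Taking the follow-up score or the change as the outcome gives the same treatment estimate, so the sponsor can keep reporting change. Apply the same adjustment to proptosis, eyelid retraction and quality of life. The sentence cannot be carried out until an analysis visit is named; that is a separate choice for the sponsor.

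The cost is one sentence and one covariate already collected, with no new visits, data or patients. The statistical price is one degree of freedom. The largest expected variance loss is 1/(N − 4): 1/36 = 2.8% with 40 analysed, or 1/30 = 3.3% with 34.
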